5.1. ADVERSE EVENTS

An AE is any unfavorable and unintended sign, symptom, or disease temporally associated with the use of an investigational medicinal product (IMP) or other protocol-imposed intervention, regardless of attribution.

This includes the following:

- AEs not previously observed in the subject that emerge during the protocol-specified AE reporting period, including signs or symptoms associated with radiation retinopathy that were not present prior to the AE reporting period.
- Complications that occur as a result of protocol-mandated interventions (e.g., endophthalmitis).

Preexisting medical conditions (other than the condition being studied) judged by the investigator to have worsened in severity or frequency or changed in character during the protocol-specified AE reporting period.

5.2. METHODS AND TIMING FOR ASSESSING AND RECORDING SAFETY VARIABLES

The investigator is responsible for ensuring that all AEs and SAEs that are observed or reported during the study are collected and reported to the FDA, appropriate IRB(s), and Genentech, Inc. in accordance with CFR 312.32 (IND Safety Reports).

5.2.1. Adverse Event Reporting Period

The study period during which all AEs and SAEs must be reported begins after informed consent is obtained and initiation of study treatment and ends 28 days following the last administration of study treatment or study discontinuation/termination, whichever is earlier. After this period, investigators should only report SAEs that are attributed to prior study treatment.

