3. STUDY DESIGN

3.1. DESCRIPTION OF STUDY

RRR is a phase II, randomized, multicenter, clinical study to assess the tolerability and efficacy of ranibizumab treatment administered in subjects with radiation retinopathy. Subjects will be randomized into one of 3 arms; ranibizumab treatment administered IVT monthly vs. ranibizumab treatment administered IVT monthly combined with peripheral targeted photocoagulation vs. ranibizumab treatment administered IVT for three months followed by as

needed treatment of ranibizumab combined with peripheral targeted photocoagulation over 48 weeks. From week 52 to week 101, all 3 treatment arms will employ a treat and extend protocol for IVT ranibizumab treatment.

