3.2. OVERVIEW OF STUDY DESIGN

There is significant scientific evidence to support the concept that radiation-mediated tissue damage involves both inflammatory cascades, as well as innate immunity of the host. This theory is very similar to the disease processes involved with age-related macular degeneration.⁴ Epithelial cells, endothelial cells, and fibroblasts participate in angiogenesis, fibrogenesis, and epithelialization to limit the damage caused by radiation to an inflamed tissue and to initiate tissue repair.⁴ The triggers for proliferative responses include free radicals and growth factors such as fibroblast (FGF), epithelial (EGF), vascular endothelial (VEGF), platelet-derived growth factors (PDGF) as well as cytokines like TNF- α and IL-1, with macrophages being a major source. Of these triggers, VEGF is the one most well understood in the eye at the present time, and thus is a logical target to limit radiation-induced damage to healthy tissues.

This trial will compare the results of 3 different combinations of therapy to assess the efficacy of peripheral targeted-retinal photocoagulation (TRP) applied to areas of retinal non-perfusion and poor-perfusion combined with ranibizumab injections for the treatment of macular edema secondary to radiation retinopathy. Specifically, this trial will evaluate the ability to reduce the monthly treatment burden by eliminating areas of peripheral ischemia as detected by wide field fluorescein angiography. This peripheral ischemic retina is likely a major VEGF production site. By selectively eliminating these ischemic areas with angiography-guided laser ablation while preserving more perfused areas of peripheral retinal, pathological levels of VEGF may be significantly reduced, translating into fewer necessary monthly intravitreal injections while preserving useful peripheral visual field. The study will include 3 cohorts followed for a total of 104 weeks.

Subjects will be randomized into one of three treatment cohorts in a 1:2:2 ratio.

Day 1 through Week 48:

- Cohort A (n=8) will receive monthly treatment of 0.5 mg ranibizumab for 48 weeks. Monthly treatment is defined as every 28 days (\pm 7 days).

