4.5.2. Early Termination Assessments

Subjects who withdraw from the study prior to completion should return for an early termination evaluation 28 days (\pm 7 days) following the last injection/study visit for monitoring of all adverse events (serious and nonserious). The schedule of assessments for early termination is the same as that for the final visit.

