APPENDIX A
Study Flow Chart – Screen through Week 48

Visit	Screen ¹	Day 0 ¹	Week 1 (±3 days)	Week 4 (±7 days)	Week 8 (±7 days)	Week 16 (±7 days)	Week 20 (±7 days)	Week 24 (±7 days)	Week 28 (±7 days)	Week 32 (±7 days)	Week 36 (±7 days)	Week 40 (±7 days)	Week 44 (±7 days)	Week 48 (±7 days)
Informed Consent	X													
Demographic Information	X	X												
Medical/ Ophthalmic History	X	X												
Inclusion/Exclusion	X	X												
Randomization	X													
Vital Signs	X	X	X	X	X	X	X	X	X	X	X	X	X	X
Concomitant Medications	X	X	X	X	X	X	X	X	X	X	X	X	X	X
Adverse Events ²	X	X	X	X	X	X	X	X	X	X	X	X	X	X
BCVA (ETDRS)	X	X	X	X	X	X	X	X	X	X	X	X	X	X
Intraocular pressure ³	X	X	X	X	X	X	X	X	X	X	X	X	X	X
SD-OCT	X	X	X	X	X	X	X	X	X	X	X	X	X	X
B-Scan	X ⁸									X				X
FA/FP	X													
Indirect Ophthalmoscopy/ Slit Lamp	X	X	X	X	X	X	X	X	X	X	X	X	X	X
TRP Laser ⁶			X ⁶						X ⁷		X ⁷			
Study Drug Injection ³		X ^{4,5}		X ^{4,5}	X ^{4,5}	X ^{4,5}	X ^{4,5}	X ^{4,5}	X ^{4,5}	X ^{4,5}	X ^{4,5}	X ^{4,5}	X ^{4,5}	X ^{4,5}

1) Visits 1 and 2 can be combined

2) AEs will be collected from the time informed consent is signed to early termination or end of study

3) Measure IOP pre-dose and 30 (± 15) minutes post-injection

4) Cohort A & B

5) Cohort C, loading dose of 3 ranibizumab injections followed by PRN injections starting at Week 12 if subject meets retreatment criteria (see Appendix E)

6) Cohort B and C

7) Cohort B and C – Additional TRP if subject meets retreatment criteria (see Appendix C)

8) Performed per standard of care at Investigator Discretion

9) Treatment interval between injections based on a treat and extend protocol

10) Mandatory visit, regardless of treatment interval

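### Section 5.2.1 closes required AE reporting 28 days after the last treatment and opens it only at first treatment, contradicting Appendix A and Section 5.2, which cover the whole study

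*Protocol*

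**What the plan says.** Four places in the protocol set a period for adverse events.

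- **Section 5.2.1.** On its opening, the text says that the period "begins after informed consent is obtained and initiation of study treatment". On its closing, the text says that it "ends 28 days following the last administration of study treatment or study discontinuation/termination, whichever is earlier". It adds: "After this period, investigators should only report SAEs that are attributed to prior study treatment".
- **Appendix A, footnote 2, in both flow charts.** "AEs will be collected from the time informed consent is signed to early termination or end of study". The Adverse Events row is marked at week 104.
- **Section 5.2.** The investigator must ensure that "all AEs and SAEs that are observed or reported during the study are collected and reported" to the FDA, the IRBs and the drug manufacturer.
- **Section 4.5.2.** Subjects who withdraw return 28 days (plus or minus 7) "following the last injection/study visit for monitoring of all adverse events (serious and nonserious").

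The timing comes from the design sections. Section 3.2 states: "The study will include 3 cohorts followed for a total of 104 weeks". Section 3.1 states: "From week 52 to week 101, all 3 treatment arms will employ a treat and extend protocol for IVT ranibizumab treatment". Under Section 3.2 the injection interval grows by one week at a dry visit, shrinks by one week on recurrence, and is capped at 12 weeks. Appendix A makes the week 104 visit mandatory and marks no injection there.

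**The concern.** A site cannot tell which end date governs. If a non-serious AE, or an SAE judged unrelated, occurs five weeks after the last injection in a subject still attending visits, Appendix A and Section 5.2 include it and Section 5.2.1 does not require it. The same doubt exists at the start. Screening may precede Day 0 by up to 14 days and includes fluorescein angiography, so a reaction to that procedure lies inside the Appendix A period and outside the 5.2.1 period.

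Other text depends on the choice. Section 5.1 identifies newly emerging AEs and worsened pre-existing conditions by reference to the reporting period. Section 5.5.2.2 makes the reporting of deaths depend on it, and cites for this a Section 5.1.2 that does not exist. SAP 6.1 then reports AEs as counts and percentages by cohort. At stake is whether those counts cover the same stretch of the trial for every subject.

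**Working it through.** The plan gives no figure for the length of the reporting period, so there is none to reproduce. The check is date arithmetic on nominal weeks.

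**Inputs.** Follow-up ends at week 104 (3.2). The 5.2.1 period ends 28 days, that is 4 weeks, after the last treatment. Treat-and-extend starts at week 52 from a four-week interval. The interval rises by 1 week if dry and falls by 1 if not, with a floor of 4 weeks and a cap of 12 (3.2). Injections continue to week 101 (3.1).

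**Formula.** Weeks lost = max(0, 104 − (week of last injection + 4)). This is positive only when the last injection is before week 100.

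**Step 1: eyes that are not dry at first and dry at every visit after that.**

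| Non-dry visits before first dry visit | Last injection (week) | Last injection + 4 | Weeks lost |
|---|---|---|---|
| 0 (52, 57, 63, 70, 78, 87, 97) | 97 | 101 | 3 |
| 1 | 101 | 105 | 0 |
| 2 | 95 | 99 | 5 |
| 3 | 99 | 103 | 1 |
| 4 | 94 | 98 | 6 |
| Never dry (every 4 weeks) | 100 | 104 | 0 |

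**Step 2: all dry and non-dry sequences, including the one-week reduction.** The maximum is 7 weeks. One path that gives it is 52, 57, 63, 70, 78, 85, 93. The next injection would be due at 93 + 9 = 102, after week 101, so the period closes at 93 + 4 = 97 and 104 − 97 = 7.

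| Longest completed interval (weeks) | Maximum weeks lost | Mean over paths (unweighted) |
|---|---|---|
| 4 | 0 | 0 |
| 5 | 4 | 0.96 |
| 6 | 5 | 1.13 |
| 7 | 6 | 1.46 |
| 8 | 7 | 1.96 |
| 9 | 5 | 2.0 |
| 10 | 3 | 1.5 |

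The means treat all paths as equally likely and do not predict what will happen.

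**Step 3: sensitivity.** Appendix A's last injection column before week 104 ends at week 100. With that as the latest injection the maximum is 9 weeks (path ending 82, 91: 104 − 95 = 9). If injections were allowed to week 103, an assumption, it is 5. If extension began at week 48, it is 7 to 8. An extra injection at the mandatory week 78 visit leaves the maximum at 7 for injections to week 101, but moves the four-weekly eye's last injection to week 98, with 2 weeks lost. The ±7-day visit windows can move any figure by up to about 2 weeks.

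**Step 4: subjects who stay in the study untreated and then leave.** Take a Cohort C eye that is dry from week 12, has no further laser, and leaves at week 40. Its last treatment was the third loading dose at week 8, so the 5.2.1 period closed at week 12, and 40 − 12 = 28 weeks are lost. A Cohort A or B subject injected on schedule and leaving in the same week loses none. A subject whose injections are held (3.4) and who leaves before they resume is in the same position. If the subject stays in and is injected again at week 52, the last treatment moves later and the year-one gap disappears.

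**Step 5: the early termination visit.** If the 5.2.1 period ends at discontinuation, a visit about 28 days after the last contact falls outside it. If the 28 days are read as applying to discontinuation as well, the period ends 28 days after the last treatment. The visit may take place on days 29 to 35, or later still when the last contact involved no injection. Some early termination visits fall outside the period on either reading.

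**The case against.** The best defence is that Appendix A governs collection and Section 5.2.1 governs reporting to outside parties. A site could then record every AE to week 104 and send on only those inside the narrower period. The safety analysis in Section 4.8.2 draws on all AEs from all 40 subjects with no window. This softens the conflict but does not remove it: Section 5.2 requires AEs during the study to be both collected and reported, and Sections 5.1 and 5.5.2.2 use the reporting period to say which new AEs and which deaths count.

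Four stronger inferences are tempting, and the documents do not support them.

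- *The eyes extended furthest lose most.* The always-dry eye, which is extended furthest, loses 3 weeks, while some eyes that reach only an 8-week interval lose 7. The average loss tends to rise with the interval, but the actual loss depends on where the last injection falls.
- *Follow-up is cut.* The week 104 visit is mandatory, with acuity, pressure, OCT, angiography and examination marked. SAEs attributed to treatment stay reportable throughout.
- *Neovascular glaucoma and vitreous hemorrhage are lost from the secondary endpoint.* Nothing ties that endpoint to the AE period. Scheduled examinations, pressure, angiography and the Appendix F grading detect these events separately.
- *Cohorts are biased against each other in year two.* All cohorts follow one treat-and-extend rule from week 52, and the documents give no sign of how their intervals would differ.

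**Conclusion.** The contradiction stands, at both the start and the end of the period. For completers last injected before week 100, required reporting of non-serious AEs and unattributed SAEs closes before week 104. On nominal dates the gap is 0 weeks for four-weekly injections, 3 for an always-dry eye, and at most 7 with the last injection by week 101 (9 if week 100 is the latest). These figures rest on a start at week 52 from a four-week interval and on visits at their target dates. For completers both readings of the closing clause give the same gap.

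Longer gaps, such as the 28 weeks illustrated, arise only for subjects who stay untreated and then leave. The documents do not say how many there would be. This is a defect in AE reporting rules that should be corrected; it does not show bias in an efficacy endpoint.

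**What to change.** Reword Section 5.2.1 to the Appendix A period: all AEs and SAEs from signed consent to the week 104 visit or the early termination visit. Keep the existing rule that SAEs attributed to study treatment remain reportable afterwards. Then align the other places:

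- Section 5.2 should point to this period.
- Section 4.5.2 should state that the early termination visit closes it.
- Section 5.5.2.2 should cite 5.2.1 instead of the missing 5.1.2.

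With this wording the gap before week 104 is 0 weeks for every completer, whatever the interval.

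Extending the period to the later of week 104 and 28 days after the last injection is not recommended. An injection at week 101 would carry it to week 105, past the last scheduled visit.

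The cost is a wording amendment and slightly more AE reporting, with no added visits.

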5.2.2. Assessment of Adverse Events

All AEs and SAEs whether volunteered by the subject, discovered by study personnel during questioning, or detected through physical examination, laboratory test, or other means will be reported appropriately. Each reported AE or SAE will be described by its duration (e.g., start and end dates), regulatory seriousness criteria if applicable, suspected relationship to ranibizumab (see following guidance), and actions taken.

5.3. EVALUATIONS

Medical and ophthalmic history will be obtained at screening visit to review body systems.

Ophthalmologic evaluations will include slit lamp examination, dilated binocular indirect high-magnification ophthalmoscopy, measurements of BCVA, intraocular pressure pre- and post-injection, and B-scan. (See Section 4.5 for a detailed description of the study assessments.)

5.4. VITAL SIGNS

Pulse and blood pressure will be measured at protocol-specified study visits (see Section 4.5).

5.5. PROCEDURES FOR ELICITING, RECORDING, AND REPORTING ADVERSE EVENTS

5.5.1. Eliciting Adverse Events

A consistent methodology for eliciting AEs at all subject evaluation timepoints should be adopted. Examples of non-directive questions include:

- “How have you felt since your last clinical visit?”
- “Have you had any new or changed health problems since you were last here?”

5.5.2. Specific Instructions for Recording Adverse Events

Investigators should use correct medical terminology/concepts when reporting AEs or SAEs. Avoid colloquialisms and abbreviations.

5.5.2.1. Diagnosis vs. Signs and Symptoms

If known at the time of reporting, a diagnosis should be reported rather than individual signs and symptoms (e.g., record only liver failure or hepatitis rather than jaundice, asterixis, and elevated transaminases). However, if a constellation of signs and/or symptoms cannot be medically characterized as a single diagnosis or syndrome at the time of reporting, it is ok to report the information that is currently available. If a diagnosis is subsequently established, it should be reported as follow-up information.

5.5.2.2. Deaths

All deaths that occur during the protocol-specified AE reporting period (see Section 5.1.2), regardless of attribution, will be reported to the appropriate parties. When recording a death, the event or condition that caused or contributed to the fatal outcome should be reported as the single medical concept. If the cause of death is unknown and cannot be ascertained at the time of reporting, report “Unexplained Death”.

5.5.2.3. Preexisting Medical Conditions

A preexisting medical condition is one that is present at the start of the study. Such conditions should be reported as medical and surgical history. A preexisting medical condition should be re-assessed throughout the trial and reported as an AE or SAE only if the frequency, severity, or character of the condition worsens during the study. When reporting such events, it is important to convey the concept that the preexisting condition has changed by including applicable descriptors (e.g., “more frequent headaches”).

5.5.2.4. Hospitalizations for Medical or Surgical Procedures

Any AE that results in hospitalization or prolonged hospitalization should be documented and reported as an SAE. If a subject is hospitalized to undergo a medical or surgical procedure as a result of an AE, the event responsible for the procedure, not the procedure itself, should be reported as the SAE. For example, if a subject is hospitalized to undergo coronary bypass surgery, record the heart condition that necessitated the bypass as the SAE.

Hospitalizations for the following reasons do not require reporting:

- Hospitalization or prolonged hospitalization for diagnostic or elective surgical procedures for preexisting conditions
- Hospitalization or prolonged hospitalization required to allow efficacy measurement for the study or
- Hospitalization or prolonged hospitalization for scheduled therapy of the target disease of the study.

5.5.2.5. Pregnancy

If a female subject becomes pregnant while receiving investigational therapy or within 90 days after the last dose of study drug, a report should be completed and expeditiously submitted to the Genentech, Inc. Follow-up to obtain the outcome of the pregnancy should also occur. Abortion, whether accidental, therapeutic, or spontaneous, should always be classified as serious, and expeditiously reported as an SAE. Similarly, any congenital anomaly/birth defect in a child born to a female subject exposed to the {study drug} should be reported as an SAE.

5.5.2.6. Post-Study Adverse Events

The investigator should expeditiously report any SAE occurring after a subject has completed or discontinued study participation if attributed to prior {study drug} exposure. If the investigator should become aware of the development of cancer or a congenital anomaly in a subsequently conceived offspring of a female subject who participated in the study, this should be reported as an SAE.

5.5.2.7. Reconciliation

The Sponsor agrees to conduct reconciliation for the product. Genentech and the Sponsor will agree to the reconciliation periodicity and format, but agree at minimum to exchange monthly line listings of cases received by the other party. If discrepancies are identified, the Sponsor and Genentech will cooperate in resolving the discrepancies. The responsible individuals for each party shall handle the matter on a case-by-case basis until satisfactory resolution.

5.5.2.8. AEs of Special Interest (AESIs)

AEs of Special Interest are defined as a potential safety problem, identified as a result of safety monitoring of the investigational product.

The ranibizumab Events of Special Interest are:

- Retinal pigment epithelial tear
- Increased intraocular pressure > 30 mmHg not responsive to maximal topical IOP-lowering drugs measured on two separate days
- Traumatic cataract
- Endophthalmitis
- Intraocular inflammation of > 2+ cell (including vitritis and uveitis)
- Retinal detachment
- ATEs, including stroke

5.5.2.9. Evaluation of Causality

To ensure consistency of AE and SAE causality assessments, investigators should apply the following general guideline:

- **Yes** – There is plausible temporal relationship between the onset of the AE and administration of the ranibizumab and the AE cannot be readily explained by the subject's clinical state, intercurrent illness, or concomitant therapies; and/or the AE follows a known pattern of response to the ranibizumab; and/or the AE abates or resolves upon discontinuation of the ranibizumab or dose reduction, if applicable, reappears upon re-challenge.
- **No** – Evidence exists that the AE has an etiology other than the ranibizumab (e.g. preexisting medical condition, underlying disease, intercurrent illness, or concomitant medication); and/or the AE has no plausible temporal relationship to ranibizumab administration (e.g. cancer diagnosed 2 days after first dose of study drug).

Expected adverse events are those adverse events that are listed or characterized in the Package Insert or current Investigator Brochure.

Unexpected adverse events are those not listed in the Package Insert (P.I.) or current Investigator Brochure (I.B.) or not identified. This includes adverse events for which the specificity or severity is not consistent with the description in the P.I. or I.B. For example, under this definition, hepatic necrosis would be unexpected if the P.I. or I.B. only referred to elevated hepatic enzymes or hepatitis.

5.5.2.10. Evaluation of Severity

The severity of an AE will be graded by the investigator using a 3-point scale (mild, moderate, or severe).

- **Mild** – dose not interfere in a significant manner with subject's normal functioning level. It may be an annoyance. Prescription drugs are not ordinarily needed for relief of symptoms, but may be given because of the personality of the subject.
- **Moderate** – produces some impairment of functioning but is not hazardous to health. It is uncomfortable or an embarrassment. Treatment for symptom (including prescription drugs) may be needed.
- **Severe** – Produces significant impairment of the functioning or incapacitation and is a definite hazard to the subject's health. Treatment for symptom may be given and/or subject is hospitalized.

